This study will assess if the rapid elimination of ketamine facilitates a short and tolerable suspension of breastfeeding. If the study determines that significant amounts of ketamine remain in breast milk after 9 hours and 3 intervals, a decision will be made to add further intervals for assessment. The collection at 3 hour intervals will continue until ketamine levels are undetectable.

No hazardous substances or procedures are involved

Pumping of breast milk will be performed by the subjects, collected, and preserved as per the lab's criteria. Every attempt will be made to collect milk in volume. The study will provide a pump for collection to each participant

Subjects may stay at the clinic for the duration of the collection , or may be provided with instructions and collection materials for at home pumping if the duration is prolonged beyond 9 hours. As much as possible, tThe samples will be collected by the next day.

Subjects will refrain from eating and drinking 3-4 hours before receiving ketamine, this to prevent stomach contents that may contribute to nausea, and reduce any risk of aspiration. Subjects are permitted one cup of coffee if they are caffeine dependent, or juice or water at 3-4 hours prior. Subjects will provide consent for fasting prior to its initiation verbally and later fully in person at the clinic.

A urine pregnancy test will be conducted prior to each administration of ketamine.

A first subject in the study will have milk collected at 0, 3, 6, 9, 12 and 15 hours to determine if these intervals are sufficient to characterize a basic pharmacodynamic profile. If there is a negligible quantity in the samples as the time frame proceeds, the lab will not analyze subsequent samples. Once determined, the study will proceed with the remaining 3 subjects at the intervals projected from the first subject

Two dosages will be administered: 0.5ml/kg and 1.0ml/kg. Intramuscularly (IM). Each administration will be separated by a minimum of 3 days and preferably one week. Each session will follow the same process and procedure as described herein and occur at the study site.

PROCEDURE TIMING CHART

HOUR	PROCEDURE
-30 minutes	Arrives at Study Site Pregnancy Test Review of IC and Fasting with Consent
-!5	BP, HR, Review of Systems
0 Hour	Zero Time Pump
15	IM 0.5mg/kg; or Second Session 1.0mg/kg
15-60	Support for Subject who is reclining on sofa with eyeshades and ambient music

1 hour	BP, HR

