- experience. Administration will be conducted in the same comfortable setting in which KAP sessions are routinely provided. Investigators are continually present throughout the time frame of this experience, however long it may persist. Subjects will remain in the office until fully recovered and will have a ride home and will not drive themselves.

- • Agitation—may occur transiently with dissociative effects. Subjects will remain in the clinical setting until ketamine’s influence has passed and they are safe to leave. We have never had to treat agitation, as it passes, and reassurance and support have been sufficient to enable attainment of calmness. In the event of unusual agitation that is a risk to the patient, sublingual lorazepam can be administered. With over 500 patients and several thousand ketamine sessions, this has never occurred.
- • Safety in operating machinery and driving—Subjects will have rides home when ready to leave.
- • No long term negative effects involving administration of ketamine in these dosages and frequencies have been reported in vast numbers over many decades of use.

A follow-up formal telephone session will occur at 4 weeks after the second administration. Questions will focus on any adverse effects on subjects or infants, difficulties in resuming breast feeding, psychological difficulties and insights not discussed in the prior 4 weeks of follow-up availability. Throughout the study, subjects will be reachable by their cell phones for emergency and consultative contact with the Investigators—who will have developed an on-call schedule.

Potential Benefits to Subjects

Ketamine administered in this clinical environment may well contribute to a sense of well-being and an exploration of consciousness. If emotional issues arise these will be fully processed. The Study Staff are skilled psychotherapists, versed in the practice of ketamine assisted psychotherapy.

Subjects may well feel they are contributing to the benefit of women who have postpartum symptoms and disorders.

Method of Subject Identification and Recruitment

Two of the investigators have close connections to practicing OB/GYNs, one being one of these himself; and the other has a practice with postpartum women in part at a local

university medical school. As only 4 subjects will take part, with the possibility of drop-out requiring further recruitment this 'n' is compatible with the outreach potential of the Investigators.

No advertising is involved.

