Costs to the Subject and Reimbursement for Participation

Subjects will not bear any costs and will be reimbursed for travel expenses to the Study Site. Subjects will receive a stipend of \$200 for participation--\$100 paid on enrollment and \$100 paid at conclusion of the second event.

Data Analysis

As data is accumulated by the laboratory, it will be presented as both absolute quantities and graphed. Subject data will be correlated with concentration in breast milk

according to age, body weight, dosage, volume of milk collected, length of breast feeding to the time of the study—months.

Data Storage and Confidentiality

Data will be inputted at the site into an Excel digital format with a matrix with subjects as specified above. No identifying data will be inputted and the study will be fully HIPPA compliant. Subjects will be coded as follows: 1A, 2B, 3C, 4D, and so on if more than 4 subjects are included in the Study. Access to this data will be restricted to Investigators and stored on a limited access backup disc. ADDED Written materials will be stored at the study site in a locked file cabinet, with access controlled by the Clinical Coordinator.

Potential Treatment for a Research Related Injury

Should a research related injury occur, subjects will have full support of the Investigators for treatment based in depth, frequency and duration on the nature of that injury. Subjects have full access to the investigators by phone and email and will be contacted in follow-up directly at 4 weeks after the last ketamine session.

The study will secure insurance specific to the possibilities arising to subjects as a result of their participation in the study--which will include medical coverage.

The IC includes language pertinent to arbitration should that be necessary to determine the responsibility of the study for an injury should it occur and there be a dispute.

References

Chang T, Glazko AJ (1974) Biotransformation and disposition of ketamine. *Int Anesthesiol Clin* 12(2):157–178

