APPENDIX C

FOLLOW-UP CALL AT 4 WEEKS

Fundamentally, this is an open conversation with subjects to ascertain the aftermath effects of the two ketamine sessions.

Questions that are included will focus on:

Any adverse effects on subjects or infants: Have you felt or noticed and problems with your physical state; or your emotional state since your ketamine sessions? If so, do you attribute these to your ketamine experiences.

Were there positive effects that you have noted?

Have you noticed any changes in your infant since your ketamine experiences? Do you attribute these to ketamine?

Difficulties in resuming breast feeding: Did you have any difficulties with your infant as a result of the suspension of breast feeding? How long did this last if there were problems? Do you have a view of how long suspension of breast feeding is tolerable to you? To your infant?

Have you experienced any psychological difficulties or insights you have not discussed in the prior 4 weeks of follow-up?

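### No question about the infant or the first breast-feeding pause is scheduled before the second, doubled injection, and the single 4-week call pools both sessions

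*Combined protocol and SAP*

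**What the plan says.** Under Potential Adverse Effects: "A follow-up formal telephone session will occur at 4 weeks after the second administration". Its content is set out in the next sentence: "Questions will focus on any adverse effects on subjects or infants, difficulties in resuming breast feeding", together with psychological matters not already discussed.

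Appendix C gives the wording. On the infant: "Have you noticed any changes in your infant since your ketamine experiences? Do you attribute these to ketamine". On the mother, it asks about problems with her physical state "or your emotional state since your ketamine sessions". It asks how long any difficulty with resuming feeding lasted, and what length of suspension is tolerable. It does not ask which session an answer refers to.

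On spacing, the Summary of Research Design and Procedures both say: "Each administration will be separated by a minimum of 3 days and preferably one week". The Procedure Timing Chart gives 0.5 mg/kg first and 1.0 mg/kg at the second session. Before each injection it lists a pregnancy test, a review of consent and fasting, blood pressure, heart rate and a review of systems.

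Procedures also states a question beyond milk concentration: "This study will assess if the rapid elimination of ketamine facilitates a short and tolerable suspension of breastfeeding".

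The section on research-related injury times the follow-up differently. Subjects "will be contacted in follow-up directly at 4 weeks after the last ketamine session".

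**The concern.** The plan names effects on infants as a follow-up topic and a tolerable pause in feeding as something it will assess. Each woman pauses feeding twice, at two doses. Yet in the visible text nobody is scheduled to ask how the infant was, or how the first pause went, until both doses have been given and about a month has passed.

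Two things are at stake:

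- **Safety information.** An infant problem after session 1 has no scheduled route to the investigators before session 2. It reaches them only if the mother raises it herself, through the on-call arrangement or in passing.
- **Interpretation.** A pooled answer recalled weeks later cannot reliably show whether a change, or a badly tolerated pause, followed 0.5 or 1.0 mg/kg. With 4 women, one lost or unassignable report is a quarter of the data.

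**Working it through.** The plan states no figure to reproduce here. The check compares the sections and does simple interval arithmetic.

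**Inputs**
- Call: 4 weeks = 28 days after the second administration (Potential Adverse Effects).
- Gap between injections: at least 3 days, preferably 7, no maximum (Procedures).
- Doses: 0.5 then 1.0 mg/kg (Procedure Timing Chart). The running text gives these in ml/kg. The units must be reconciled, but the ratio is the same either way.
- Feeding may resume at 18 hours for the first subject (Methods, item 2).
- 4 women, 2 sessions each.

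**Arithmetic**
1. Dose ratio: 1.0 / 0.5 = 2.
2. Recall for session 2: 28 days.
3. Recall for session 1 = 28 + gap: 28 + 3 = 31 days at the minimum gap, 28 + 7 = 35 days at the preferred gap. It is longer if the gap exceeds a week.
4. Possible feeding time before injection 2 = gap − 18 h: 72 − 18 = 54 h at 3 days, 168 − 18 = 150 h at 7 days. This assumes that the 18 hours run from dosing, that they apply to the woman concerned, and that feeding does resume between sessions. No infant question is scheduled in that time.

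**What is scheduled before the second injection**

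| Topic | Scheduled? | Where |
|---|---|---|
| Maternal BP, HR, review of systems | Yes, before each injection | Timing Chart |
| Maternal BP and HR after session 1 | Yes, at 1 h and 3 h | Timing Chart |
| Acute maternal effects in session 1 | Observed by investigators | Potential Adverse Effects |
| Infant changes since session 1 | No | – |
| How the session 1 pause was tolerated | No | – |
| Documented review of effects since session 1 | Not beyond the maternal review of systems and vitals | – |

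The documents describe no adverse-event log. Data Analysis lists milk concentration against age, weight, dose, milk volume and months of breast feeding, with no safety or tolerability item.

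**Who gets the call.** Potential Adverse Effects counts from the second administration, and Appendix C speaks of two sessions. The injury section counts from the last session. The Informed Consent section lets a woman withdraw before the second injection. If she does, the first rule gives her no call date and the last one does.

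**Does feeding resume between sessions?** Methods lets the first subject resume at 18 hours. The Informed Consent section says infants will not be breast-fed for the study period, which could mean each session or the whole study. The screening script refers only to the study session. Infant exposure after session 1 depends on which applies.

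**The case against.** A reader might infer that maternal effects also go unreviewed until the 4-week call. The documents do not support that. A review of systems with blood pressure and heart rate precedes each injection, and Procedures says every session follows the same process. Investigators also stay with the woman until she has recovered.

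A reader might likewise infer that no effect could ever be tied to a dose. That is too strong. Women can reach the investigators throughout, a report made between sessions would date itself to session 1, and Appendix C is framed as an open conversation. What stands is that nothing prompts or records such a report.

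It is also tempting to express the delay as a multiple of the drug's elimination time. That comparison misleads: feeding is suspended during that time, so it is not the period in which an infant effect would appear. The useful figures are the recall times.

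Three further points on the other side:

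- Staff do contact women who go home early, but the stated purpose is to prompt pumping. Sample pickup is not described as a conversation and does not occur for every woman.
- The stated objective is ketamine in milk, and tolerability in Appendix C is asked as a matter of duration. This limits the importance of the point. But the plan does say it will assess tolerable suspension, and each pause belongs to one session.
- The consent form is not in the text available, so it may contain reporting instructions. The point is therefore confined to the visible text.

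**Conclusion.** The point holds for the infant and for the pause in feeding. No scheduled enquiry about either takes place between the first injection and a second one of twice the dose, which may follow in 3 days. On the mother's side, cover before that injection is limited to blood pressure, heart rate and a review of systems. The one scheduled call comes 28 days after session 2 and 31 to 35 days after session 1 at the stated gaps, and it pools the two. Infant changes and tolerability cannot reliably be assigned to a session or dose.

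The size of any infant risk is not established here. It depends on whether feeding resumes between sessions, which the documents leave unclear. If it does not resume, exposure between sessions falls away, but the pause is longer and its tolerability still goes unasked before session 2. The mismatch between second and last session is minor: the two coincide for women who complete, and it matters only for one who stops after a single injection.

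This is an inexpensive improvement that should be made. It does not affect the milk measurements.

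**What to change.** 1. At the −30 minute arrival for session 2, ask and record the Appendix C infant, breast-feeding and maternal questions about session 1, with onset and duration. An investigator documents that the answers were seen before the second injection.
2. After each session, once feeding has resumed, ask the same questions: at home pickup where there is one, otherwise by a short call.
3. Keep the 4-week call, but word its questions separately for each session.
4. In Potential Adverse Effects and Appendix C, time the call from the last injection received, as the injury section already does, so that women who stop after one injection are included.
5. Reconcile Methods, the Informed Consent section and the screening script on whether breast feeding resumes between sessions.

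These changes add enquiry and documentation only. They set no dose, stopping or feeding rule.

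Cost: at most 4 question sets at session 2 arrival (one per woman) and 4 × 2 = 8 post-session contacts, using questions largely written already. That is a few minutes per session, a wording change to the protocol and, for women without home pickup, a new short call.

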Subjects will refrain from eating and drinking 3-4 hours before receiving ketamine, this to

prevent stomach contents that may contribute to nausea, and reduce any risk of aspiration. Subjects are permitted one cup of coffee, juice or water at 3-4 hours prior if they are caffeine dependent. PROVIDED IN LAST VERSION

- 1) A urine pregnancy test will be conducted prior to each administration of ketamine.
- 1)
- 2) A first subject in the study will have milk collected at 0, 3, 6, 9, 12 and 15 hours to determine if these intervals are sufficient to characterize a basic pharmacodynamic profile. If there is a negligible quantity in the samples as the time frame proceeds, the lab will not analyze subsequent samples. Once determined, the study will proceed with the remaining 3 subjects at the intervals projected from the first subject. The lab will process the samples from the first subject as rapidly as possible to enable continuation of the study. Breast milk will be collected until ketamine levels are undetectable. If significant amounts of ketamine are found in samples from the 3 subsequent subjects at the last interval determined by the profile of the first subject, additional time frames for collection will be added. If necessary, the process will be repeated to fully document pharmacokinetics.

As real time testing of ketamine content in breastmilk is not possible, the first subject will be the exemplar for the timing of the resumption of breast feeding based on the data obtained, such as not detectable at 9 hours, hence breast feeding may resume. For that first subject, breast feeding may resume at 18 hours, which corresponds to 9 half-lives for ketamine, 4 half-lives being the accepted timing for the absence of a molecule. This will be confirmed by lab testing as quickly as possible for the first subject.

- 3) Pumping of breast milk will be for a full expression so as not to influence concentrations in subsequent sampling intervals. The volume of breast milk will be quantified for each expression.
- 4) Milk will be refrigerated in sterile containers and aliquots of one ounce will be brought to the lab refrigerated as soon as possible. A second aliquot of each

expression will be frozen in the event of loss or spoilage of the first aliquots, site to be determined.

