1. 5) Each aliquot will be labelled with coded subject designation, concentration of ketamine administered, date, and interval. The lab will be provided with the actual quantity of ketamine administered to each subject at the 0.5 and 1.0mg/kg levels and the weight of each patient in kgs.
 - 1)
1. 6) The Lab will provide the data to KRF in formats suitable for journal publication.

INTAKE FORM ATTACHED

AS PREVIOUSLY INDICATED THERE ARE NO QUESTIONNAIRES BEING ADMINISTERED— THIS WAS DELETED FROM THE PRIOR REVISION

Inclusion Criteria

- Age 21-45
- Postpartum with established lactation for a minimum of 3 months.
- Ability to pump breast milk and to provide a reservoir for infant feeding prior to the study; or acceptance of bottle feeding by the infant.
- In good health—normal BP/P; afebrile-temp ascertained; review of systems by MD; absence of diagnosed illnesses.
- Not pregnant--Pregnancy tested for before each administration by urine assay.

Exclusion Criteria:

- Hypertension with a BP greater than 145/90
- Absence of all psychiatric medications specifically; medications and supplements, or evaluated by the PI for non-interference
- No alcohol or other substances such as marijuana for 72 hours or more.
- Weight <50kg or > 90kg.
- Pregnancy

Potential Adverse Effects

- • Nausea and vomiting—a less than 5% incidence of intolerability to ketamine.
- • Transient hypertension—BP will be monitored. In clinical practice, and in this age group, this has not occurred with any frequency.
- • Ketamine is a dissociative anesthetic and subjects have a high likelihood of experiencing dissociative effects during the first two hours following ketamine's administration. Generally, the major impact occurs in the first hour, with full recovery to baseline by 3 hours. The Investigators have conducted thousands of sessions in which dissociative effects are part of the ketamine assisted

psychotherapy (KAP) approach, including at much higher doses than those being administered in this study. Subjects may experience, an altered mental state in which there is an imaginative stream of associations, sensations and imagery. There can be anxiety accompanying a shift from ordinary reality. The Investigators have specialized in developing a transformative psychotherapy with utilization of this state and are fully equipped and experienced in dealing effectively with this state. Subjects will be prepared for the possibility of this

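### If the planned correlations are calculated as coefficients, those for age, weight and months of lactation rest on four women; per-woman listings and within-woman dose ratios would use the data better

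*Combined protocol and SAP*

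**What the plan says.** Data Analysis is two sentences long. The first says of the laboratory data that "it will be presented as both absolute quantities and graphed". The second says "Subject data will be correlated with concentration in breast milk" and names five factors for this: the woman's age, her weight, the dosage, the milk volume and the months she has been breast feeding. No coefficient, test, unit of analysis or concentration summary is named, nor any handling of repeated samples.

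Other sections show what will be available:

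- **Number of women.** Summary of Research Design plans four. Data Storage and Confidentiality provides subject codes for four, "and so on if more than 4 subjects are included in the Study", without giving a larger number.
- **Doses.** Each woman has two sessions, one at each dose level (Summary of Research Design; Procedures). The Procedure Timing Chart attaches the higher level to the second session.
- **Volume.** Methods item 3: "The volume of breast milk will be quantified for each expression".
- **Dose given.** Methods item 5: "The lab will be provided with the actual quantity of ketamine administered to each subject", together with her weight.
- **Unanalysed samples.** Methods item 2: once the quantity is negligible, "the lab will not analyze subsequent samples".
- **Storage.** The data go into a spreadsheet, "a matrix with subjects as specified above".

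**The concern.** Listing and graphing suit a small descriptive study whose stated purpose is to measure the presence and concentration of ketamine in milk. The second sentence of Data Analysis is the difficulty. Age, weight and months of lactation hardly change between sessions a few days apart, so the independent unit for these factors is the woman, and four are planned. A coefficient from four points says almost nothing, yet a published r of 0.8 could be taken to show that milk levels depend on the mother's age, weight or stage of lactation.

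Dosage is a different case. It varies within each woman, so she can serve as her own control. The plan does not say that the comparison will be made that way. It matters because Summary of Research Design relies on a roughly linear pattern of blood concentrations to estimate milk concentrations above the higher dose level. Each woman's pair of sessions is the study's only direct evidence on whether milk follows that pattern.

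**Working it through.** The documents give no power, precision, alpha or variability figure, so there is nothing of the plan's own to reproduce. Steps 1 to 3 apply only if Pearson coefficients are calculated, with two-sided 0.05 assumed.

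**1. Size of r needed at n = 4.** The critical value is t / √(n − 2 + t²), with t on n − 2 degrees of freedom.
- n = 4: t = 4.303, so 4.303 / √(2 + 18.51) = 0.950.
- n = 6, an assumed enlargement: t = 2.776, so 2.776 / √(4 + 7.71) = 0.811.
- A rank correlation on four women cannot reach 0.05. Its smallest two-sided p is 2/4! = 2/24 = 0.083.

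**2. Large coefficients by chance.** The inputs are one concentration summary per woman, normal data and no true association. Convert r = 0.8 to t = r√(n − 2) / √(1 − r²).
- n = 4: t = 0.8 × 1.414 / 0.6 = 1.886 on 2 df, so P(|r| > 0.8) = 0.200. For at least one of three factors, assumed independent, 1 − 0.8³ = 0.488.
- n = 6: t = 0.8 × 2 / 0.6 = 2.667 on 4 df, so P = 0.056. For at least one of three, 1 − 0.944³ = 0.159.
- If the true correlation is 0.5 (assumed), simulation at n = 4 gives |r| above 0.95 in about 9% of studies and the wrong sign in about 20%.

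**3. More samples do not help.** Three post-dose times in two sessions give 3 × 2 = 6 samples per woman, 24 in all. If these are treated as independent, the type I error for a woman-level factor rises from 5% to about 24%, 35% or 45% at assumed intraclass correlations of 0.3, 0.5 and 0.7 (simulation).

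**4. Dosage and weight.** The relation depends on how dosage is expressed, which Data Analysis does not say.
- In mg, within one session: dose = k × kg. Summary of Research Design gives 25 to 50 mg at 50 kg and 35 to 70 mg at 70 kg, that is 25/50 = 35/70 = 0.5 and 50/50 = 70/70 = 1.0. Planned dose is proportional to weight, r = 1.
- In mg, over both sessions: the median r is about 0.38, with four weights assumed uniform over the eligible 50 to 90 kg.
- Per kg: every woman receives both levels, so dosage is unrelated to weight, r = 0.

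**5. Precision of a within-woman ratio.** Around an observed dose-normalised ratio of 1, the 90% interval is exp(± t × √2 × s / √n), with s = √ln(1 + CV²). The documents give no within-woman CV; 30% is assumed first.
- s = √ln(1.09) = 0.294. Four pairs: t = 2.353 on 3 df, exponent 2.353 × 1.414 × 0.294 / 2 = 0.489, interval 0.61 to 1.63.
- Four pairs at CVs of 20% and 50%: 0.72 to 1.39 and 0.46 to 2.19.
- Three pairs at 30%: 0.50 to 2.01.

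**The case against.** The strongest reply is that the plan never commits to a coefficient. Setting concentration against age, weight and dosage can mean tabulating it, and the subject matrix in Data Storage and Confidentiality comes close to the listing recommended here. This stands, and it is why the point is conditional. It does not remove the point, because the matrix is described as data storage rather than as a reported result, and the verb used in Data Analysis invites a coefficient.

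A second reply is that the dose ratio gains little, being wide with four pairs and tied to session order. This also stands, so the ratios are for display and not for inference. They still show whether each woman's milk levels scale with dose, which a correlation pooled over women does not.

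A third reply is that *absolute quantities* is a small gap, since the purpose statement and the next sentence of Data Analysis both speak of concentration. That is fair. Defining the term is a clarification, not the correction of an error.

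A reader might also infer stronger claims that the documents do not support:

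- **That dose and body weight cannot be separated.** This holds only for mg within a single session (step 4).
- **That decisions on further collection intervals or on resuming breast feeding rest on these correlations.** Procedures and Methods item 2 tie them to whether ketamine is still found in milk.
- **That skipping later samples seriously distorts the amounts.** The laboratory stops only when quantities are negligible, so it is enough to say which samples were not analysed.

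**Conclusion.** The concern holds in conditional form and is minor. If the correlations become coefficients, those for age, weight and months rest on four women and cannot be interpreted: |r| must exceed 0.95 for p < 0.05, and a chance value above 0.8 for at least one of the three is about as likely as not (49%). The chance figures assume normal data, one concentration summary per woman and independent factors. Six women would bring the 49% down to 16%, but the documents commit to no number above four.

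Apart from that condition, the plan does not state a within-woman dose comparison that its design already provides. The study's main aim and its operational decisions are unaffected; what is at stake is how the results are reported and read.

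**What to change.** Reword Data Analysis in three respects:

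(a) List age, weight and months of lactation beside each woman's results, without coefficients or p-values.

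(b) Replace the dosage correlation with each woman's ratio between her two sessions at matched times, dose-normalised by the mg actually given, and show every ratio. Label it descriptive, because the Procedure Timing Chart ties the higher dose to the second session and dose is confounded with order.

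(c) Report concentration, and concentration × volume per expression, for ketamine and norketamine, stating which samples were undetectable or not analysed.

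The cost is plan wording, a few spreadsheet columns and a record of each sample's status. No additional sample, visit or participant is needed. The downside is that any interval placed on the ratio will be wide (step 5), so it should be optional.

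Separately, and not a precondition for (a) to (c), the dose units conflict. Summary of Research Design and Procedures state the two dosages in ml/kg, while the Procedure Timing Chart and Methods item 5 use mg/kg. At the 100 mg/ml stock given under Safety, 0.5 ml/kg × 100 mg/ml = 50 mg/kg against 0.5 mg/kg, a 100-fold difference, and the same factor applies to the higher level. These statements must be reconciled.
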